4 STUDY ASSESSMENT DATA SOURCES

The BENEFIT-02 Study collected pain assessments, questionnaires, paresthesia perception assessments, and other data, both remotely and in-office. Table 2 provides an overview of the study assessment data sources stratified by assessment type (in-office vs. remotely collected).

Table 1: Study Assessment Data Sources

Source	Assessment Type	Description
Study Source Documentation Worksheets/ Electronic Capture Database (EDC) Data	In-office Assessment	
Datasets contain in-office pain assessments, questionnaires, paresthesia perception assessments, and other data collected via study worksheets and other source documents that are uploaded and have each required data point entered in the EDC by study personnel.
 
For analysis, this data is extracted directly from the EDC.

Subject Diary	Remote Assessment	
Datasets consist of paper-based Subject Diary data, including information regarding pain medication usage, Numerical Rating Scale (NRS) for Pain score and Patient Global Impression of Change logged by subjects during the study.
 
Paper-based Subject Diary scans are uploaded in EDC, but each data point is not entered directly by study personnel. Therefore, Subject Diary data will require transcription by sponsor personnel for analysis.

CamNtech PRO-Diary Watch	Remote Assessment	
Datasets consist of acute NRS scores, pain events, pain medication events, sleep quality, and activity data electronically logged by subjects that is collected via the study data collection watch.
 
Files containing this electronically collected data are uploaded in the EDC by study personnel, for later systematic analysis.

In-office data is used for analysis of the study primary and secondary endpoints (See Section 6.1 and Section 6.2) while analysis of additional data of interest (See Section 7) may include both in-office and remotely collected data. Further details for data collected for the study can be found in the study protocol.

5 SAMPLE SIZE ANALYSIS

The BENEFIT-02 Study is designed to limit the number of subjects involved and the duration of intervention, while ensuring sufficient preliminary data regarding the effectiveness and safety of the study SCS therapies is collected in order to accomplish the study objectives.

Since the effect size of each study SCS therapy on the primary outcome measure (NRS for overall pain) is unknown, statistically driven sample size estimation is not possible. A reduction of approximately two points on an NRS for chronic pain represents a clinically relevant difference.¹

In order to detect a difference of approximately two in mean change in NRS pain score (from baseline to the final study visit) between the two study SCS therapies, a target of 70 subjects should complete the 12 day study stimulation period (~35 subjects for each study SCS therapy).

Therefore, to account for expected attrition due to subject withdrawal following consent but prior to completion of the study testing period:

- Up to 226 subjects will be provisionally enrolled
 - Assumed 51% drop out rate between consent and the randomization visit (e.g. failed commercial trial, withdrawn consent, etc.)
- Approximately 110 subjects will undergo randomization (fully enrolled)
 - Assumed 15% drop out rate following randomization prior to initiation of the assigned study SCS therapy (e.g. subject doesn't meet post-washout inclusion criteria)
- Approximately 93 subjects will initiate the randomly assigned study SCS therapy
 - Assumed 25% drop out rate following initiation of the randomly assigned study SCS therapy (e.g. non-compliance with study assessment schedule, withdrawn consent, subject lost to follow-up, etc.)
- Approximately 70 subjects will complete the study testing period

¹ J. T. Farrar *et al.*, "Clinical importance of changes in chronic pain intensity measured on an 11-point numerical pain rating scale," *Pain*, vol. 94, pp. 149-158, Nov 2001.

6 STUDY ENDPOINTS

The BENEFIT-02 Study includes the assessment of two primary endpoints and two secondary endpoints that are designed to provide preliminary information regarding the effectiveness and safety of the two study SCS therapies under investigation. There are no formal tests of hypotheses or other pre-specified statistical tests associated with the study primary endpoints.

6.1 Primary Endpoints

6.1.1 Primary Endpoint 1

The purpose of primary endpoint 1 is to evaluate the change since baseline in Numerical Rating Scale (NRS) for pain (overall) for each study SCS therapy.

The evaluation of primary endpoint 1 will be based on the NRS for pain (overall) obtained at the final study testing visit (NRS_{Final}) compared with the baseline measurement obtained prior to initiation of the commercial trial therapy (NRS_{Baseline}) (Note: NRS_{Baseline} data collection may occur on the same date as the trial lead implant), for subjects randomized to each study SCS therapy.

Primary endpoint 1 analyses include all subjects with measurements for both NRS_{Final} and NRS_{Baseline}; therefore, subjects must have completed the study to be included in the primary endpoint 1 analyses.

Subject's re-assigned and/or re-programmed to receive the alternative therapy during the study testing period will be excluded from primary endpoint 1 analyses.

6.1.2 Primary Endpoint 2

The purpose of primary endpoint 2 is to provide an inter-therapy comparison of change since baseline in Numerical Rating Scale (NRS) for pain (overall). The evaluation of primary endpoint 2 will be based on a comparison of the results of primary endpoint 1 between the two study SCS therapies.

Primary endpoint 2 analyses include all subjects included in primary endpoint 1 analyses. Therefore, subject's re-assigned and/or re-programmed to receive the alternative therapy during the study testing period will be excluded from primary endpoint 2 analyses.

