Subjects who do not experience the required increase in NRS for overall pain during the washout period, or are non-compliant with the study assessment schedule (e.g. do not complete the required phone call following the two day period), will not have the randomly assigned study SCS therapy initiated. These subjects will be exited from the study.

Following the conclusion of the washout period, subjects who are eligible to participate in the study testing period will have the randomly assigned study SCS therapy initiated. The study SCS therapy will be administered for 12 days, during which time phone calls scheduled with the subject, site personnel, and sponsor

personnel will occur up to once per day. During these phone calls, the study SCS therapy will be optimized via sponsor-directed subject reprogramming of the study stimulator and study data will be collected.

An initial study-specific in-office visit will occur six to eight days following randomization, and a final in-office visit will occur 14 days following randomization, at which time the subject's SCS trial lead(s) will be disconnected from the BIOTRONIK wearable study stimulator, and the subject's participation in the study will end.

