2.1 STUDY ENDPOINTS

This clinical study includes the assessment of two primary endpoints and two secondary endpoints that are designed to provide preliminary information regarding the effectiveness and safety of the two study SCS therapies under investigation. Since the effect size of each study SCS therapy on the primary outcome measure (Numerical Rating Scale (NRS) for pain (overall) [7]) is unknown, there are no formal tests of hypotheses or other pre-specified statistical tests associated with the study primary endpoints.

2.1.1 Primary Endpoint 1

The purpose of primary endpoint 1 is to evaluate the change since baseline in Numerical Rating Scale (NRS) for pain (overall) for each study SCS therapy.

The evaluation of primary endpoint 1 will be based on the NRS for pain (overall) obtained at the final study testing visit (NRS_{Final}) compared with the baseline measurement obtained prior to initiation of the commercial trial period (NRS_{Baseline}), for subjects randomized to each study SCS therapy.

Primary endpoint 1 analyses will include all subjects with measurements for both NRS_{Final} and NRS_{Baseline}.

2.1.2 Primary Endpoint 2

The purpose of primary endpoint 2 is to provide an inter-therapy comparison of change since baseline in Numerical Rating Scale (NRS) for pain (overall).

The evaluation of primary endpoint 2 will be based on a comparison of the results of primary endpoint 1 between the two study SCS therapies. Primary endpoint 2 analyses will include all subjects included in primary endpoint 1 analyses.

2.1.3 Secondary Endpoint 1

The purpose of secondary endpoint 1 is to evaluate the change in Numerical Rating Scale (NRS) for pain (overall) since conclusion of the commercial trial for each study SCS therapy.

The evaluation of secondary endpoint 1 will be based on the NRS for pain (overall) obtained at the final study testing visit (NRS_{Final}) compared with the measurement obtained following conclusion of the commercial trial but prior to initiation of the randomized study SCS therapy (NRS_{Commercial Trial}), for subjects randomized to each study SCS therapy.

Secondary endpoint 1 analyses will include all subjects with measurements for both NRS_{Final} and NRS_{Commercial Trial}.

2.1.4 Secondary Endpoint 2

The purpose of secondary endpoint 2 is to collect preliminary safety information regarding the investigational device and study SCS therapies (stimulation parameters are within the ranges of existing commercial therapies).

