3.1 Study Participation Status Definitions

Screen failure – Subject that is unsuitable for enrollment following protocol required laboratory/psychological assessments or implanted with SCS trial lead(s) that are incompatible with the study stimulation system. These subjects will be exited from the study once screen failure is confirmed. Subject informed consent forms will be kept in the site's administrative files.

Provisionally enrolled – Subject who is fully informed about the specifics of the study by authorized site personnel and provides informed consent by properly signing an informed consent form after confirmation of the initial enrollment criteria.

Fully enrolled (Randomized) – Provisionally enrolled subject who meets all clinical eligibility criteria, and has been randomized. These subjects will be followed in accordance with the protocol requirements.

Study exit - Early termination of study participation applicable to subjects that have signed an informed consent form.

Study completion - Subject who completes all protocol-required study procedures.

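### Both documents limit the primary NRS analyses to subjects with a final-visit score, the available text gives no missing-data method, and the SAP also drops re-assigned subjects

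*SAP*

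**What the plan says.** Protocol 2.1.1 bases primary endpoint 1 on the "NRS for pain (overall) obtained at the final study testing visit (NRS_{Final}) compared with the baseline measurement" taken before the commercial trial. On who is analysed it says: "Primary endpoint 1 analyses will include all subjects with measurements for both" the final and the baseline score. SAP 6.1.1 repeats this rule and adds: "therefore, subjects must have completed the study to be included in the primary endpoint 1 analyses". In both documents primary endpoint 2 uses the same subjects.

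Four other places bear on the point:

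- **Timing of the final score.** Protocol 1.1 says that "a final in-office visit will occur 14 days following randomization". Participation ends at that visit.
- **Meaning of completion.** SAP 3.1 defines a completer as a "Subject who completes all protocol-required study procedures".
- **Expected loss.** SAP 5 plans for about 110 randomised, 93 starting the assigned therapy and 70 completing. For the last step it states: "Assumed 25% drop out rate following initiation of the randomly assigned study SCS therapy".
- **Switched subjects.** SAP 6.1.1 and 6.1.2 remove anyone re-assigned or re-programmed to the other therapy. Protocol 2.1.1 and 2.1.2 contain no such exclusion.

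SAP 6.3 evaluates the changes with paired and two-sample t-tests at p < 0.05, although SAP 6 disclaims formal hypothesis testing on the primary endpoints.

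**The concern.** Whether a subject has a final score is decided after randomisation and, for most of those lost, after the study therapy has begun. Subjects with poor relief or poor tolerance may be more likely to stop, and subjects doing badly may be more likely to be switched. If so, those who remain are a favourable selection. Mean improvement in each arm (primary endpoint 1) would then be too large, and the reported standard error would give no sign of it. The inter-therapy comparison (primary endpoint 2) would be distorted as well if the selection worked differently in the two arms.

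The supplementary analyses do not fill the gap. The arm comparison in SAP 7.5 is again limited to subjects who complete the study. The phase comparison in SAP 7.4 is optional, pools the two therapies and needs data in every interval. Yet SAP Table 10 shows an in-office NRS at the midpoint visit (Study OV2), which the primary analysis leaves unused.

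**Working it through.** **1. The plan's attrition figures (SAP 5).**

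- Randomised: 226 × (1 − 0.51) = 110.7; plan 110.
- Starting assigned therapy: 110 × (1 − 0.15) = 93.5; plan 93.
- Completing: 93 × (1 − 0.25) = 69.75; plan 70.

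The figures reproduce.

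**2. Who has no final score.**

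- Before therapy starts: 110 − 93 = 17, or 17/110 = 15.5% of those randomised.
- After therapy starts: 93 − 70 = 23, or 23/93 = 24.7% of starters.
- Together: 40/110 = 36.4% of those randomised.

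The final score is taken only at the day-14 visit, so the loss is the same under the protocol rule and the SAP sentence. The 17 leave before receiving the assigned therapy (SAP 5 gives failure of the post-washout criterion as an example), so their loss cannot reflect response to it. The 23 are the group that matters for bias.

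**3. The added exclusion of switched subjects.** Neither document gives a switching rate. For assumed rates x among the 70 completers, 70 × (1 − x) remain:

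| x (assumed) | Remaining | Lost, of 93 starters | Lost, of 110 randomised |
|---|---|---|---|
| 0% | 70 | 24.7% | 36.4% |
| 5% | 66.5 | 28.5% | 39.5% |
| 10% | 63 | 32.3% | 42.7% |
| 20% | 56 | 39.8% | 49.1% |
| 30% | 49 | 47.3% | 55.5% |

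**4. Possible bias within an arm.** Let p be the share of starters who stop and d the amount by which their mean improvement falls short of the completers'. The all-starter mean is (1 − p) × C + p × (C − d), where C is the completer mean, so the completer mean is too large by p × d. With p = 0.25 from the plan and d assumed:

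- d = 1.5: 0.25 × 1.5 = 0.375 points.
- d = 2: 0.25 × 2 = 0.50 points.

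That is 19% to 25% of the 2-point difference that SAP 5 calls clinically relevant. The plan gives no SD. At an assumed SD of 2.5 to 3.0 with 35 per arm, the standard error of an arm mean is SD/√35 = 0.42 to 0.51, so the bias is about 0.7 to 1.2 standard errors.

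**5. Possible bias between arms.** This is pA × dA − pB × dB. With a common d = 2 (assumed):

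- 30% against 20% stopping (assumed): 0.10 × 2 = 0.2 points.
- 35% against 15% stopping (assumed): 0.20 × 2 = 0.4 points.

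The standard error of the difference is SD × √(2/35) = 0.60 to 0.72 at the same SDs. The bias is below one standard error in both cases, and zero if stopping is alike in the two arms.

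**The case against.** A reader might infer that the SAP's completion sentence narrows the protocol's analysis set, and that this is why more than a third of randomised subjects are lost. The documents do not support that. The SAP draws completion as a consequence of the same two-score rule. An early leaver has no final score under either document, and Protocol section 2 itself plans for 110 randomised and 70 completing. Deleting the sentence would recover almost no one. What remains is a wording problem: under the SAP 3.1 definition, a subject with both scores but some other procedure missed could be excluded. No number attaches to that, and the SAP's phrasing suggests it is not intended. SAP 6.2.1 uses the same final score for secondary endpoint 1 with no completion wording.

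It can also be said that:

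- The shortfall of 1.5 to 2 points and the unequal stopping rates have no source in the documents. This stands. The reasons that SAP 5 gives as examples for post-initiation loss are non-compliance, withdrawn consent and loss to follow-up. Poor relief is not named, though withdrawn consent does not rule it out.
- The absence of a missing-data method can be stated only of the text available. The protocol text stops at 2.1.5, its contents list a figure on the primary endpoint analysis that is not shown, and the SAP refers to the protocol for further detail. This also stands.
- The midpoint visit falls six to eight days after randomisation, so four to six days into therapy. Anyone who stops sooner has no in-office score on therapy, and a mixed model adds little for them. This limits the remedy without removing the case for it.
- The study is a feasibility study seeking preliminary information. That lowers the severity, but the planned p-values mean that the results will still be read as evidence of effect.

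**Conclusion.** The concern holds as a complete-case problem common to both documents, made somewhat worse by the SAP's own exclusion of switched subjects. The planned loss among therapy starters is about 23 of 93, before any loss through switching. The 36% of randomised subjects is correct arithmetic, but it mixes in about 17 who never start the assigned therapy and should not be quoted as the scale of the bias.

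The overstatement of about 0.4 to 0.5 points per arm depends wholly on the assumed shortfall in stoppers. It would be nil if stopping were unrelated to relief. Primary endpoint 1 is the more exposed of the two, because primary endpoint 2 is affected only if stopping, or the shortfall among those who stop, differs by therapy. All counts are planning assumptions, not observed losses. Must-fix is not supported for a feasibility study with assumed bias sizes; the change is recommended.

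**What to change.** In SAP 6.1:

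1. Add an analysis of all subjects who started their randomised therapy, analysed as randomised and including those later switched. Use a repeated-measures mixed model with in-office overall NRS at baseline, midpoint (OV2) and final visit all as outcomes. Treating baseline as an outcome, not a covariate, keeps starters without a midpoint score in the model. Report the completer analysis beside it.
2. Add one sensitivity analysis for subjects who stop: either a delta shift that makes their imputed final scores worse by stated amounts, or baseline carried forward. The latter counts stoppers as unchanged, so with 23 of 93 stopping it would multiply the completer mean improvement by 70/93 = 0.75.
3. State openly that the exclusion of re-assigned and re-programmed subjects departs from Protocol 2.1.1, give the reason, and report the number excluded per arm.
4. Reword the completion sentence so that having both scores is the operative rule, for example: *subjects are included if both scores are recorded, whether or not every other study procedure was done.*

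The cost is SAP wording and one model with one sensitivity analysis, on data already planned. The mixed model assumes that scores are missing at random, and subjects who stop before OV2 contribute little, which is why item 2 is needed. Keeping switched subjects in their randomised arm can dilute a true difference between therapies, so the analysis with and without them should be shown.

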6.2 Secondary Endpoints

6.2.1 Secondary Endpoint 1

The purpose of secondary endpoint 1 is to evaluate the change in Numerical Rating Scale (NRS) for pain (overall) since conclusion of the commercial trial for each study SCS therapy.

The evaluation of secondary endpoint 1 will be based on the NRS for pain (overall) obtained at the final study testing visit (NRS_{Final}) compared with the measurement obtained following conclusion of the commercial trial but prior to initiation of the randomized study SCS therapy (NRS_{Commercial Trial}), for subjects randomized to each study SCS therapy.

Secondary endpoint 1 analyses will include all subjects with measurements for both NRS_{Final} and NRS_{Commercial Trial}.

Subject's re-assigned and/or re-programmed to receive the alternative therapy during the study testing period will be excluded from secondary endpoint 1 analyses.

6.2.2 Secondary Endpoint 2

The purpose of secondary endpoint 2 is to collect preliminary safety information regarding the investigational device and study SCS therapies (stimulation parameters are within the ranges of existing commercial therapies).

The evaluation of secondary endpoint 2 will be based on the adverse event-free rate (AEFR), calculated based on the total number of subjects free from any AEs classified by the investigator as clearly related to the investigational device. AEs that are resolved without any medical procedure or surgical intervention (e.g. through device reprogramming) will not be included in the analysis of secondary endpoint 2. The observed AEFR will be presented, along with a summary of all reported secondary endpoint 2 adverse events.

$$\text{Adverse event-free rate (AEFR)} = \frac{\text{(Number of subjects without an investigational device-related AE)}}{\text{(Total number of subjects)}}$$

Evaluable subjects for secondary endpoint 2 will include all subjects who undergo randomization and have the investigational stimulation system connected to their SCS trial lead(s).

6.3 Endpoint Results Example Tables and Figures

The results of primary and secondary endpoints will be analyzed as described in this Statistical Analysis Plan and the Clinical Protocol for the BENEFIT-02 Study.

Example tables and figures representative of how the data will be presented in the final study results are provided below. As applicable, descriptive statistics may also be used to present and summarize the data collected during the study. Means and standard error of the mean will be used to describe results from primary endpoints 1 and 2, and secondary endpoint 1. Change in NRS and Percent Pain Relief (PPR) will be evaluated using paired T-test or two-sample T-test, as applicable. For all analyses, $p < 0.05$ is considered significant. Frequency distributions will be used to describe secondary endpoint 2.

6.3.1 Primary Endpoint 1

Figure 2: Therapy A/B Change in NRS for Pain (Overall) Since Baseline

[figure not shown]
[figure not shown]

Table 2: Primary Endpoint 1 Summary

Numerical Rating Scale for Pain (Overall)	Therapy A n = XX	Therapy B n = XX	Total (A+B) n = XX
Mean NRS at Baseline \pm SEM	X.X \pm X.XX	X.X \pm X.XX	X.X \pm X.XX
Mean NRS at Final Study Visit \pm SEM	X.X \pm X.XX	X.X \pm X.XX	X.X \pm X.XX
Mean Change in NRS \pm SD	X.X \pm X.XX	X.X \pm X.XX	X.X \pm X.XX
Paired T-Test (Final Mean NRS vs Baseline)	p = 0.XXX	p = 0.XXX	-----

Figure 3: Percent Pain Relief (PPR) per Therapy**Table 3: Percent Pain Relief (PPR)**

Percent Pain Relief	Therapy A n = XX	Therapy B n = XX	Therapy (A+B) n = XX
Mean PPR \pm SEM	XX.X% \pm X.XX%	XX.X% \pm X.XX%	XX.X% \pm X.XX%

6.3.2 Primary Endpoint 2

Figure 4: Inter-therapy Comparison

[figure not shown]

Table 4: Inter-therapy Comparison of Change since Baseline

Primary Endpoint 2	Two-Sample T-Test on NRS	Two-Sample T-Test on Percent Pain Relief (PPR)
p value: equal var	X.XXXX	X.XXXX
p value: unequal var	X.XXXX	X.XXXX

6.3.3 Secondary Endpoint 1

Table 5: Secondary Endpoint 1 Summary

Numerical Rating Scale for Pain (Overall)	Therapy A n = XX	Therapy B n = XX	Total (A+B) n = XX
Mean NRS at Study Visit 1 \pm SEM	X.X \pm X.XX	X.X \pm X.XX	X.X \pm X.XX
Mean NRS at Study Visit 3 \pm SEM	X.X \pm X.XX	X.X \pm X.XX	X.X \pm X.XX
Mean Change in NRS \pm SEM	X.X \pm X.XX	X.X \pm X.XX	X.X \pm X.XX
Paired T-Test (Visit 3 Mean NRS vs Visit 1)	p = 0.XXX	p = 0.XXX	-----

6.3.4 Secondary Endpoint 2

Table 6: Investigational Device-Related Adverse Events

Adverse Event Type	Number of AEs	Subjects with AE, n	Subjects with AE, %
Event type 1	X	X	X.XX%
Event type 2	X	X	X.XX%
Event type 3	X	X	X.XX%
Event type 4	X	X	X.XX%
Total	X	X	X.XX%

Number of subjects = XX

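### Primary endpoint 2 is reported as four unranked p-values with no A–B difference or interval in Table 4; one named comparison, adjusted for baseline NRS and given with its 95% CI, would be a cheap improvement

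*SAP*

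**What the plan says.** SAP 6.1.2 defines primary endpoint 2 as the comparison between therapies of change in overall NRS since baseline. PPR is not part of that definition. The analysis set is that of primary endpoint 1: "Primary endpoint 1 analyses include all subjects with measurements for both NRS_{Final} and NRS_{Baseline" are both available, minus subjects switched to the other therapy. Every analysed subject therefore has a baseline NRS.

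On testing, SAP section 6 states: "There are no formal tests of hypotheses or other pre-specified statistical tests associated with the study primary endpoints". Protocol 2.1 gives the reason (unknown effect size) and says the same: "there are no formal tests of hypotheses or other pre-specified statistical tests associated with the study primary endpoints".

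SAP 6.3 nevertheless plans tests: "Change in NRS and Percent Pain Relief (PPR) will be evaluated using paired T-test or two-sample T-test, as applicable". It adds a threshold: "For all analyses, $p < 0.05$ is considered significant". For description it says: "Means and standard error of the mean will be used to describe results from primary endpoints 1 and 2".

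Table 4 in SAP 6.3.2 has two columns, a two-sample t-test on NRS and one on PPR. It has two rows, equal variance and "p value: unequal var". Its four cells are all p-values. Table 2 gives n and the mean change with its SD for each therapy.

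**The concern.** Three things are left open for the one comparison that randomisation supports.

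- **Which p-value counts.** PPR stands beside NRS change under the heading of a primary endpoint, and the 0.05 rule covers both. A PPR result below 0.05 could be reported as significant for an endpoint defined on NRS change.
- **What the estimate is.** A feasibility study with unknown effect size is most useful for an A–B difference and its uncertainty. Table 4 gives neither.
- **Whether baseline is used.** Baseline NRS enters only through subtraction or division. As a covariate it could narrow the interval, and it would remove the effect of an observed baseline imbalance.

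In addition, the statements that no tests are pre-specified do not fit with named tests and a significance threshold.

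**Working it through.** **The plan's own figures.** SAP section 5 gives 226 × 0.49 = 110.7, 110 × 0.85 = 93.5 and 93 × 0.75 = 69.75, so the chain to about 70 completers (35 per arm) reproduces. The loss after randomisation is (110 − 70)/110 = 36%. No SD or power accompanies the 2-point difference. Solving SD = 2 × √(35/2)/(z for α + z for power) gives 2.99 at 80% power and 2.58 at 90%.

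**Assumptions.** The documents give no SD or correlation. I assume baseline SD (sb) 1.5 or 2, final SD (sf) 2 or 2.5, baseline–final correlation r = 0.3, 0.5 or 0.7 (12 cells; r = 0.6 added in the table below), 35 per arm and two-sided 0.05.

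**1. Effect of the covariate.** Var(change) = sb² + sf² − 2·r·sb·sf. Var(ANCOVA) = sf²(1 − r²), multiplied by 1 + 1/(N − 4) = 1 + 1/66 (1.5%) for the covariate. The variance columns omit this 1.5%; power includes it and comes from the noncentral t (68 and 67 df) for a 2-point difference.

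| sb/sf, r | Var(change) | Var(ANCOVA) | Reduction | Power, change → ANCOVA |
|---|---|---|---|---|
| 2/2, 0.3 | 4 + 4 − 2.4 = 5.60 | 4 × 0.91 = 3.64 | 35.0% | 93.6% → 99.0% |
| 2/2.5, 0.3 | 4 + 6.25 − 3 = 7.25 | 6.25 × 0.91 = 5.69 | 21.6% | 86.5% → 92.9% |
| 2/2.5, 0.5 | 4 + 6.25 − 5 = 5.25 | 6.25 × 0.75 = 4.69 | 10.7% | 94.9% → 96.6% |
| 1.5/2.5, 0.5 | 2.25 + 6.25 − 3.75 = 4.75 | 4.69 | 1.3% | 96.6% → 96.6% |
| 1.5/2.5, 0.6 | 2.25 + 6.25 − 4.5 = 4.00 | 6.25 × 0.64 = 4.00 | 0% | 98.5% → 98.3% |

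The gain vanishes when r is near sb/sf.

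**2. Interval width with a robust standard error.** This was simulated with integer NRS, baseline mean 7 limited to 4–10, and final mean 4 limited to 0–10 (all assumed). HC3 standard errors were used with N − 3 df. Mean 95% CI half-width, unequal-variance t to HC3 ANCOVA:

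- 2/2, r = 0.3: 1.07 → 0.93
- 2/2.5, r = 0.3: 1.21 → 1.12
- 1.5/2.5, r = 0.5: 1.00 → 1.02

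Over the 12 cells the change runs from about −13% to +3%. The interval narrows by about 7% or more in 4 cells and changes by less than 3% in the other 8. In 4 of those 8 it is 2–3% wider. Simulated power in the three cells listed goes from 94.9% to 98.6%, 86.1% to 91.1% and 96.0% to 95.8%. The 2 points here are a shift applied before rounding and limiting to 0–10, so the realised difference is a little smaller.

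**3. Baseline imbalance.** If one arm starts 0.5 points higher, its apparent extra pain reduction is 0.5 × (1 − r·sf/sb). At 2/2, r = 0.3 this is 0.5 × 0.70 = +0.35. At 1.5/2.5, r = 0.7 it is 0.5 × (1 − 1.167) = −0.08.

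**4. Four p-values, no true difference.** The simulated chance of p < 0.05 at 35/35 is:

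- NRS change, either variance version: 4.8–5.2%
- HC3 ANCOVA: 4.4–4.7%
- at least one of the four: 6.4–7.5%

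Almost all of the excess comes from PPR. PPR is significant while NRS change is not in 1.5–2.5% of null trials, and in about 5–9% of trials with a 1-point shift.

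**5. Unequal arms.** At 40/25, with final SD 2 and 3 and the larger SD in the smaller arm, the rates are: pooled t 6.7%, unequal-variance t 5.1%, pooled-variance ANCOVA 7.0%, HC3 ANCOVA 4.8%, any of four 9.0%. The variance version matters only in such a case, and the unequal-variance t-test already handles it.

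**The case against.** The case against is substantial, and much of it stands.

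- **The planned test is sound.** The unequal-variance t-test on NRS change holds its level, and in the scenarios above it already has at least 86% power for 2 points. This is accepted in full.
- **NRS change already ranks first by definition.** SAP 6.1.2 makes PPR supportive by implication. That is a fair reading, but Table 4 and the 0.05 rule do not say it.
- **The interval can be recovered.** Table 2 gives n, mean change and SD per arm, so a reader can work out the unadjusted difference and its unequal-variance 95% CI. The tables are called examples, and SAP 6.3 allows further descriptive statistics. The omission is thus one of presentation.
- **Some material is not available here.** SAP Figure 4, the protocol's endpoint-analysis figure and the protocol text after 2.1.5 are not in the supplied documents. Both absence claims carry that limit: no interval is claimed for Table 4 only, and no covariate for the supplied text only.
- **It may be late.** The SAP was written for the 2020 Final Report and describes data collection in the past tense. If A–B results had been seen, a newly added ANCOVA cannot lead.

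A reader might infer that four p-values mean a false-positive rate near 1 − 0.95⁴ = 18.5%. The documents do not support this: the four tests are strongly correlated, and no text lets any one of them suffice. A reader might also infer that ANCOVA is sure to narrow the interval. In 8 of the 12 assumed cells it makes almost no difference.

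**Conclusion.** The point holds as a modest improvement in reporting and precision. It is not an error in the planned test or a failure of error control. What rests on the documents alone is that Table 4 ranks none of its four p-values and shows no A–B difference or interval, that PPR lies outside the endpoint definition, and that SAP 6.3 conflicts with SAP section 6 and protocol 2.1 on whether tests are planned.

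The precision gain rests wholly on assumed SDs and correlations: a half-width change of about −13% to +3%, with a clear gain in 4 of 12 cells. The 6–8% false-positive rate applies only under an any-of-four rule that no text states.

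A reader might infer that baseline adjustment makes the comparison a fully randomised one. It does not. Both analyses describe completers who were not re-assigned, after an expected 36% loss from randomisation and before switched subjects are removed.

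**What to change.** 1. In SAP 6.3.2, name one main analysis for primary endpoint 2: ANCOVA of final NRS on randomised therapy and baseline NRS, with the standard error fixed in advance (for example HC3). Lead with the adjusted A–B difference and its 95% CI.
2. Show the unequal-variance t-tests on NRS change and on PPR as supportive, without a significance label. Drop the equal-variance row.
3. Make SAP section 6, SAP 6.3 and protocol 2.1 agree on whether tests are planned and what the 0.05 rule covers.
4. State that the result describes completers who were not re-assigned.

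If A–B results had already been seen when the SAP is changed, keep the difference in mean NRS change with its unequal-variance 95% CI as the main analysis and label the ANCOVA post hoc. The same unadjusted analysis serves if no covariate is wanted.

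The cost is SAP and protocol wording plus one regression, with no new data, visits or subjects. Making ANCOVA the main analysis is this cheap only before A–B results are seen. Where the correlation is near the ratio of baseline to final SD, the price of the robust adjusted analysis is an interval 2–3% wider.
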